8.6 Unanticipated problems

Unanticipated problems (ANP) are considered situations that pose risks to the participating subjects, generally any incident, experience or result that meets all of the following criteria:

- Unexpected in terms of its nature, severity, or frequency in relation to: 1) study-related documents such as the investigator's manual, study protocol, and informed consent form; and 2) the characteristics of the study population.
- Related or possibly related to your participation in the study (possibly related means that there is a reasonable possibility that the incident or results were caused by study procedures).
- Indication that the research places participants at greater risk of harm (including physical, psychological, economic, or social) than previously recognized.

8.6.1 UAPs Report

The PI will be responsible for reporting UAPs to the sponsor, the IC, and the IEC. The report should contain the following information:

- Study identification: protocol title and number, name of the PI and, where applicable, the center.
- Detailed description of the event, incident, experience or outcome.
- Explanation, justification of the reasons why the incident represents a UAP.
- Description of changes to the protocol or corrective actions taken or proposed in response to the UAP.

UAPs that are EAS must be reported to the IEC/ CI and the sponsor within the first 24 hours of the PI becoming aware of it.

Any other UAP will be reported to the IEC/CI and the sponsor within the first 5 business days after the PI becomes aware of it.

9. Study monitoring

The study sponsor is responsible for monitoring the study. Monitoring activities include, but are not limited to: general safety monitoring, general study quality monitoring, study site monitoring, adverse event detection monitoring, reporting and follow-up, monitoring to resolve data entry discrepancies, etc.

Responsibility for monitoring activities and ultimate responsibility for monitoring rests with the sponsor.

The details of the monitoring activities are specified in a separate document from this protocol in a Monitoring Plan.

9.1 Monitoring of study centers

The research centers participating in the study will be monitored. At least one initial visit and one closing visit must be conducted for each center, although one or more follow-up visits may be required between these two mandatory visits.

The initial visit must be conducted before the first participant is enrolled at that center. During this visit, the monitor will verify that the materials to be used during the study have been received and that the personnel involved in study activities have been trained in the study. The monitor will also verify compliance with applicable regulatory requirements and standard operating procedures.

At the follow-up visit(s), the monitor will review the study documents to confirm that the research protocol and applicable standard operating procedures are being followed, that data entry is complete and timely, and that adverse event reporting is being conducted appropriately. At each visit, the monitor will discuss the findings with the investigator and determine the appropriate actions to be taken.

The closing visit will take place at the end of the study, once the last participant at the site has been discharged from follow-up. During this visit, the monitor will verify that the site has all necessary documentation for archiving, that all biological samples have been analyzed, that all PI (used and unused) has been returned to the sponsor, and that all unused materials have been recovered.

Details of monitoring are set out in the relevant plan.

9.2 Audit and quality control

To ensure compliance with GCPs and all applicable regulatory requirements, Laboratorios Sophia, S.A. de C.V. may conduct quality assurance audits. Regulatory agencies may also conduct a regulatory inspection of this study.

Details of the audit process are set out separately in an Audit Plan.

9.2.1 Pre-study audit

The study centers included in the study will be subject to a feasibility visit prior to center selection, where they will be verified to meet the minimum requirements indicated by the sponsor.

9.2.2 Audit during the conduct of the study

They may take place at any time before, during, or after the conclusion of the study. If an audit or inspection is conducted, the investigator and the institution must agree to allow the auditor/inspector direct access to all relevant documents and must allocate their time and staff time to the auditor/inspector to discuss the findings and any pertinent issues. If the audit has not been scheduled by the sponsor, the center must notify Laboratorios Sophia, S.A. de C.V. immediately.

10. Statistical analysis

10.1 Data analysis

10.1.1 Statistical analysis

Statistical analysis will be performed by staff of Laboratorios Sophia, S.A. de C.V. The statistical software SPSS version 19.0 for Windows (IBM Corporation, Armonk, NY, USA) will be used.

Although the study design is open-label, to avoid potential interpretation bias, the staff assigned to the statistical data management will be blinded to the intervention groups. Coding will be performed using consecutive numbers for each intervention group.

The data will be collected and organized in an Excel spreadsheet (Microsoft® Office). The data will then be exported to the SPSS software platform. Variables will be categorized according to their nature; see **Table 3**.

10.1.2 Data interpretation

The results of continuous quantitative variables will be presented in measures of central tendency: mean, standard deviation and ranges.

KS and SW tests will be performed, as applicable, to determine whether the distribution presents normality in the results obtained in each study group. [44]

If normality of the data is observed ($p > 0.05$; for KS and SW), the statistical analysis of the continuous quantitative variables to find significant differences (p) will be as follows:

- Intra-group analysis: will be determined using the Student's t-test for repeated measures.
- Between-group analysis: differences between groups will be analyzed using Student's t-test for independent groups.

For $p < 0.05$ in KS and SW, the statistical analysis of continuous quantitative variables to find significant differences (p) will be as follows:

- Intra-group analysis: will be determined using the Wilcoxon rank test. [45]
- Between-group analysis: differences between groups will be analyzed using the Mann-Whitney U statistic.

The level of difference to consider significance will be an α of 0.05 or less [46].

The results of the nominal and ordinal qualitative variables will be presented in frequencies, proportions and percentages.

Statistical analysis to identify significant differences in qualitative variables will be performed by creating 2x2 contingency tables and will be carried out as follows:

- Intra-group differences: will be determined by the McNemar test [47], which is applied to 2x2 contingency tables with a dichotomous trait and pairs of matched subjects to determine whether the marginal frequencies of row and column are equal (marginal homogeneity).
- Difference between groups: Differences between groups will be analyzed using Pearson's X^2 test or Fisher's exact test when expected values are less than 5.

The level of difference to consider significance will be an α of 0.05 or less.

For the reporting of adverse events, participants who were randomly assigned to an intervention group after application of the investigational product will be considered.

The final results report will be displayed in tables or graphs, as appropriate.

The investigational product will be considered safe when there are no clinical and statistical differences in all primary outcome variables, with respect to its comparator (Healon EndoCoat®).

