Investigational product, dosage and route of administration:

- PRO-149. Sodium hyaluronate 3%. Viscoelastic solution in a pre-filled syringe. Laboratorios Sophia, S.A. de C.V.
- Posology: Enough to create the desired intraocular space and perform the required intraocular maneuvers.
- Route of administration: Intraocular, in the anterior chamber.

Comparator product, dose and route of administration:

- Healon® EndoCoat. Sodium hyaluronate 3%. Viscoelastic solution in a pre-filled syringe. Johnson & Johnson Vision Surgical.
- Posology: Enough to create the desired intraocular space and perform the required intraocular maneuvers.
- Route of administration: Intraocular, in the anterior chamber.

Duration of treatment:	Approximate duration of the subject in the study:
Transsurgical.	45 days.

Evaluation criteria:

Primary outcome variables:

- Changes in CEC density.
- IOP.

Secondary outcome variables:

- Incidence of adverse events (AEs).
- Changes in corneal thickness.
- Cellularity in AC.
- Flare in AC.
- Best corrected visual acuity (BCVA).

[figure not shown]
Exploratory outcome variables:

- Investigator's report of the transsurgical evaluation.

Statistical methodology:

Data will be expressed with measures of central tendency: mean and standard deviation for quantitative variables, while qualitative variables will be presented as frequencies and percentages. The Kolmogorov-Smirnov (KS) and Shapiro-Wilk (SW) tests will be performed to determine whether the distribution is normal for the results obtained in each study group ($p > 0.05$). If normality is observed in the data, the Student's t-test for independent groups will be used to evaluate differences between groups on quantitative variables, while intragroup differences will be analyzed using the Student's t-test for repeated measures. If $p < 0.05$ for both KS and SW, the statistical analysis will be performed using the Mann-Whitney U test for differences between groups on quantitative variables, while intragroup differences will be analyzed using the Wilcoxon rank test. Differences between qualitative variables will be analyzed using the χ^2 (chi-square) test or Fisher's exact test. An $\alpha \leq 0.05$ will be considered significant.

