2.2.1 Efficacy of the investigational product

The efficacy of various SH-containing OVDs has been established in several clinical studies. A multicenter, double-blind, randomized clinical study was conducted with the Healon® EndoCoat OVD, which contains the same concentration of SH as PRO-149, in 400 patients undergoing phacoemulsification and IOL implantation.

Two hundred patients were assigned to the Healon® EndoCoat group and 200 to the control group, corresponding to Viscoat®. Efficacy was measured by CEC protection. Healon® EndoCoat demonstrated non-inferiority when compared to Viscoat® in the CEC count from pre-surgery to 3 months post-surgery ($p < 0.0001$, 1-tailed t-test, $\delta = 5\%$). The mean percentage changes observed were -4.7% for Healon® EndoCoat and -7.0% for Viscoat® with a percentage point difference of 2.3 (90% confidence interval: [0.23, 4.33]). [21]

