3.2 Specific objectives

- To compare the safety of OVD PRO-149 versus Healon® EndoCoat in cataract phacoemulsification surgery and intraocular lens implantation, through changes in pre and postoperative CEC density.
- To compare the safety of OVD PRO-149 versus Healon® EndoCoat in cataract phacoemulsification surgery and intraocular lens implantation, through changes in IOP.

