7.4 Outcome variables

7.4.1 Primary outcome variables

- Changes in CEC density.
- IOP.

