7.4.4 Definition of variables, methods and scales to be used for measurement

Variable	Guy	Unit (symbol)	Measurement method	Normal value	Evaluation time	Statistical test
Of outcome primary						
Endothelial cell count (cornea)	Continuous quantitative	Cells / mm^2	Microscopy speculate	1500-3500	VE and VF	Student t - test Mann-Whitney U Wilcoxon ranks *
Intraocular Pressure	Continuous quantitative	mmHg	Goldmann tonometry	10-21	VE, V1, V2 and VF	Student t test Mann-Whitney U Wilcoxon ranks *
Of outcome secondary						
Events adverse	Discreet	Number of cases (n)	Counting	0	VE, VP, VC, V1, V2 and VF	Student t test Mann-Whitney U*

Events adverse (Bis)	Nominal categorical	Present / Absent	Observation	Absent	VE, VP, VC, V1, V2 and VF	χ^2 or Fisher's exact test
Changes in corneal thickness	Continuous quantitative	μm	Corneal pachymetry	545 ± 40	VE and VF	McNemar test **
Cellularity of the anterior chamber	Qualitative ordinal	Degrees	Biomicroscopy	0= None	VE, V1, V2 and VF	χ^2 or Fisher's exact test
Flare in the anterior chamber	Qualitative ordinal	Degrees	Biomicroscopy	0= No flare	VE, V1, V2 and VF	McNemar test **
AVMC	Discreet	Fraction (-)	Snellen chart	0.6-2.0	VE, V1, V2 and VF	χ^2 or Fisher's exact test
Of outcome exploratory						
Transsurgical evaluation	Qualitative ordinal	Bad (0) / Very good (5)	Observation	...	VC	χ^2 or Fisher's exact test

BCVA, best-corrected visual acuity; ScrV, scrutiny visit; SurV, surgery visit; SchV, scheduling visit; V1-2, 1st / 2nd safety visits; VF, final visit; χ^2 , Chi-square; *For KS/SW, p < 0.05; **When applied

Table 3. Operational definition of variables

The variables, method, and scales used to measure them are described in detail below. They are listed in order according to **Table 3**.

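### The primary between-arm comparisons are unadjusted and chosen by a normality gate with gaps; one prespecified baseline-adjusted ANCOVA per outcome is a near-free improvement, but the IOP visit and CEC scale must be fixed separately.

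*Combined protocol and SAP*

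**What the plan says.** Section 10.1.2 sets the gate: "KS and SW tests will be performed, as applicable, to determine whether the distribution presents normality in the results obtained in each study group". If both normality tests give p above 0.05, "Between-group analysis: differences between groups will be analyzed using Student's t-test for independent groups". If both give p below 0.05, Mann-Whitney is used. The synopsis (1.1) has the same non-parametric condition: "for both KS and SW, the statistical analysis will be performed using the Mann-Whitney U test for differences between groups". The Table 3 footnote (7.4.4) shortens it to "For KS/SW, p < 0.05". None of the three places covers a mixed result, and none uses a baseline covariate.

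For IOP, the specific objective (3.2) compares the products in "cataract phacoemulsification surgery and intraocular lens implantation, through changes in IOP". The outcome lists in 1.1 and 7.4.1, and Table 3, say only IOP. Table 3 and the schedule in 1.3 place IOP at screening and at three postoperative visits (days 1, 8 and 29). No visit is primary and there is no summary across visits.

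For CEC, the quantity is a change: "Changes in CEC density" in 7.4.1 and "through changes in pre and postoperative CEC density" in 3.2, from screening to the single final-visit measurement. Table 3 gives the unit as cells per square millimetre. The planning loss and 5% margin in 10.2.2 are in percent, as is the comparator result in 2.2.1: "The mean percentage changes observed were -4.7% for Healon® EndoCoat and -7.0% for Viscoat".

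Section 10.1.2 then calls the product safe if no primary outcome shows a clinical or statistical difference from the comparator, each test being at 0.05.

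**The concern.** The safety conclusion depends on these tests. Where the test and the IOP visit are left open, two analysts who both follow the protocol can reach different verdicts on the same data. In a trial of 28 to 36 eyes, leaving out a baseline value that is already in hand also gives up precision at no saving. A false difference at any one IOP visit could deny the safety label to a product that does not differ; a visit chosen afterwards could grant it.

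**Working it through.** **Inputs.** Eyes per arm: 14 evaluable, 18 after losses (10.2.2). The losses step reproduces: 14/(1 − 0.20) = 17.5, rounded up to 18. How the 14 was derived is a separate matter and is not relied on here. Significance level 0.05 (10.1.2). The documents give no SD, distribution or correlation for CEC or IOP, so all shapes and correlations (ρ = 0.3 to 0.9) below are assumptions.

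**1. How often the gate gives no answer.** Shapiro-Wilk and Lilliefors-corrected Kolmogorov-Smirnov were simulated in each arm at 0.05. A trial counts as undefined unless all four results agree.

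| Data | n = 14 | n = 18 |
|---|---|---|
| Normal | 13.6% | 14.5% |
| Gamma(4), raw values | 39.6% | 47.8% |
| Gamma(4), change scores, latent ρ 0.7 | about 22% | about 28% |

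Across latent ρ of 0.5 to 0.8 and both sample sizes, change scores gave 19-20% for gamma(8), 22-29% for gamma(4) and 37-48% for lognormal(0.5). Change scores are the relevant quantity for CEC and, under the objective, for IOP. If Shapiro-Wilk alone governs, the arms still differ in about 8-10% of normal-data trials.

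**2. Whether it changes the verdict.** The trial was undefined and the t-test and Mann-Whitney verdicts differed in 0.2-2.8% of trials with no true difference. With an assumed 0.8 SD difference, on the literal reading, this was 1.3-1.5% for normal data and 3.2-14.1% for skewed data. These runs used raw values, which are more skewed than change scores.

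**3. Three IOP visits.** Three independent tests would give 1 − 0.95³ = 14.3%. With baseline and visits equally correlated, any two change scores have correlation (1 − ρ)/[2(1 − ρ)] = 0.5. Simulated at ρ 0.3 to 0.7, the chance of at least one false difference in change was 12.6-13.1% at n = 14 and 12.1-12.7% at n = 18. ANCOVA at all three visits gave 12.6-14.4%; ANCOVA at one named visit gave 4.6-5.5%.

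**4. What baseline adjustment gains.** With equal variance before and after surgery, ANCOVA variance relative to the change score is (1 − ρ²)/[2(1 − ρ)] = (1 + ρ)/2. Estimating one slope multiplies this by 1 + 1/(N − 4): 1 + 1/32 = 1.031 at N = 36, and 1 + 1/24 = 1.042 at N = 28.

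- ρ = 0.3: 0.65 × 1.031 = 0.67 and 0.65 × 1.042 = 0.68.
- ρ = 0.9: 0.95 × 1.031 = 0.98 and 0.95 × 1.042 = 0.99.
- Break-even: ρ = 2 × 32/33 − 1 = 0.94 at N = 36, and 2 × 24/25 − 1 = 0.92 at N = 28.

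The gain is therefore about 33% down to 1%. In simulation with normal, lognormal, gamma and exponential data, ANCOVA held type I error at 4.2-5.1%.

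**5. Change versus final value.** With baseline as covariate, the adjusted arm difference is the same for final value and absolute change, so the IOP wording conflict stops mattering. This does not extend to percent change. For CEC, unadjusted tests on absolute and percent change disagreed in 0.9-2.6% of trials with no true difference and in 4-11% at 0.8 SD, assuming baseline mean 2500, SD 250 or 400 and mean loss 7%.

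**The case against.** Much of the case on the other side stands. The synopsis and 10.1.2 state the same condition, and the Table 3 footnote may only abbreviate it. The words *as applicable* in 10.1.2 may mean that one normality test is chosen, which would remove conflicts between the two tests; disagreement between arms would remain. The objective does name change for IOP, and the bare label elsewhere can be read as a variable name. Requiring no difference at every visit is a coherent safety rule, though the plan does not state it. The trial is a pilot, and adjustment is not needed for validity.

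Blinding of the statistical staff (10.1.1) limits discretion but does not end it: absence of a difference is the favourable result whichever arm is which, so an analyst blinded only to labels can still see which choice produces it.

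A reader might infer several stronger things that the documents do not support:

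- That ANCOVA alone closes every gap. It does not select a visit.
- That IOP has no defined quantity at all. Section 3.2 names change; the defect is inconsistent wording and no primary visit.
- That most trials with skewed data would have no defined test. Rates as high as 72% arise for strongly skewed raw values, whereas the endpoints are mainly changes.
- That the gate undermines the conclusions or the type I error of a single comparison. Its effect on verdicts under no difference is small, and unadjusted tests are valid under randomization.

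**Conclusion.** The point holds as a low-cost improvement. The plan assigns no test to mixed normality results, leaves the IOP visit open and ignores baselines it already collects. The gate is undefined in about 14% of normal-data trials and roughly 20-50% with skewed change scores, but changes under 3% of verdicts when there is no true difference. The open IOP visit matters more: about a 12-13% chance of at least one false difference if change is tested at all three. ANCOVA reduces variance by about 1-33% against the change score for normal data; the gain is only 1-2% at ρ = 0.9 and gone above about 0.92-0.94. All these sizes rest on assumed shapes and correlations, so confidence is medium. The benefit is precision and reproducibility, not a repair of type I error. Nor does it repair the rule that reads non-significance as safety.

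**What to change.** In 10.1.2, 1.1 and Table 3, replace the normality gate for the primary between-arm comparisons with one prespecified ANCOVA per outcome, with arm and baseline value as terms. Report the adjusted difference with a 95% confidence interval, and keep Mann-Whitney on the change as a sensitivity analysis: under the heaviest skew tried it had more power than ANCOVA (0.94 versus 0.87).

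Separately, the sponsor must:

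- name in advance one primary IOP visit, or a single summary across visits;
- state whether CEC change is absolute or percent. If the 5% margin is to be used, restate it on that scale, since 10.2.2 applies it through a formula for a proportion.

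If the gate is kept, the minimum repair is one sentence assigning every mixed result to one named test, the same wording in all three places, and the IOP quantity, IOP visit and CEC scale stated.

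The cost is amended wording and one degree of freedom per model, a variance penalty of 3.1% (N = 36) to 4.2% (N = 28). No new data are needed. If percent CEC loss is unrelated to baseline, that penalty buys no precision for CEC.

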2.2.2 Safety of the investigational product

In the same clinical study described above, safety was evaluated by the cumulative rate of intraocular pressure (IOP) peaks ≥ 30 mmHg and the presence of adverse events (AEs).

The results demonstrated that the percentage of subjects with IOP spikes in the Healon® EndoCoat group was not higher than that in the Viscoat® group (cumulative percentage of subjects with IOP ≥ 30 mmHg during the study ($p = 0.0003$, $\delta = 0.13$, 90% confidence interval [-1.74, 7.72]).

Surgical complications reported were 3% (6/200) in the Healon® EndoCoat group and 8% (16/200) in the Viscoat® group.

Regarding AEs, 39 subjects reported an AE during the study. None of these were considered unexpected. Ninety-two percent of the AEs were IOP ≥ 30 mmHg; the incidence of this AE was 10.5% in the Healon® EndoCoat group and 7.5% in the Viscoat® group. The three AEs that did not correspond to an increase in IOP included: one subject in the Healon® EndoCoat group who developed cystoid macular edema (requiring treatment) and two subjects in the Viscoat® group: one subject who required IOL exchange for haptic damage and one who underwent removal of an ocular surface foreign body. None of the above AEs were considered related to OVD use. [21]

List of incidents or adverse reactions reported with a 3% sodium hyaluronate viscoelastic or with the use of intraocular sodium hyaluronate: [21] [22]

- Eye inflammation (iritis, hypopyon, endophthalmitis)
- Increased intraocular pressure
- Corneal edema
- Secondary glaucoma
- Corneal decompensation

All of the described incidents or adverse reactions may potentially occur with the use of PRO-149 or Healon® EndoCoat. [21] [22]

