7.4.4.2 Intraocular pressure

Tonometry is the objective measure of IOP, based primarily on the force required to flatten the cornea, or the degree of corneal depression produced by a fixed force. Goldman tonometry is based on the Imbert-Fick principle. [34]

Tonometry will be performed after instillation of topical anesthetic with fluorescein and the use of a cobalt blue filter (after assessing surface staining). Two readings will be taken, and the average will be recorded in the clinical record. The average will be recorded in the eCRF.

Management as AE: IOP peaks ≥ 30 mmHg should be reported as AE.

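### The 'safe' rule rests on a mmHg comparison of IOP, while eyes reaching 30 mmHg or more are counted only within a pooled secondary adverse-event outcome; with 18 eyes per arm, non-significance says little about spikes

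*Combined protocol and SAP*

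**What the plan says.** Section 7.4.1 names two primary outcomes, change in endothelial cell density and IOP. Table 3 (section 7.4.4) defines IOP as "Continuous quantitative mmHg Goldmann tonometry 10-21 VE, V1, V2 and VF", with Student's t, Mann-Whitney U and Wilcoxon as the tests. No visit or peak summary is named for the comparison between arms. Section 10.1.2 gives the test: "Between-group analysis: differences between groups will be analyzed using Student's t-test for independent groups" if the data look normal, Mann-Whitney U if not.

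The conclusion is also set in 10.1.2: "The investigational product will be considered safe when there are no clinical and statistical differences in all primary outcome variables, with respect to its comparator". What would count as a clinical difference is not defined.

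Pressure spikes appear in three other places:

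- Section 7.4.4.2: "IOP peaks ≥ 30 mmHg should be reported as AE".
- Section 2.2.2, on the cited comparator trial: "safety was evaluated by the cumulative rate of intraocular pressure (IOP) peaks ≥ 30 mmHg", together with adverse events. That trial had 200 patients per arm. The rates were 10.5% with Healon EndoCoat and 7.5% with Viscoat, and δ was 0.13.
- Table 3, in the secondary adverse-event rows: a count of events, and a row typed "Nominal categorical Present / Absent Observation Absent" and compared by chi-square or Fisher. Neither row separates pressure spikes from other events.

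**The concern.** The pressure harm that the protocol identifies is an eye crossing a threshold, and the only clinical evidence it cites on comparator pressure safety is expressed that way. The analysis that decides the IOP part of the safety conclusion compares means or ranks of mmHg. The spike rate by arm is not specified as a result, and it does not enter the decision.

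A few eyes with high readings move the centre of 18 values only modestly, and a rank test discounts how high those readings are. The trial could therefore report no IOP difference and declare the product safe while the data remain compatible with a much higher spike rate, and no planned output would show the reader how much higher.

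**Working it through.** **What can be reproduced.** The plan has no power figure for IOP; section 10.2.2 uses only the percentage fall in endothelial cell count. The cited trial's figures in 2.2.2 agree with each other: 0.105 × 200 = 21 and 0.075 × 200 = 15 spikes, and 36 of 39 = 92%, as stated.

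**Inputs from the documents.** 18 eyes per arm (10.2.1); significance level 0.05, taken as two-sided because the plan does not say; comparator spike rate 10.5% (2.2.2).

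**Assumptions.** The documents give no IOP mean, SD or shape. The 10.5% is a cumulative rate from another trial, applied here to a single visit. Two patterns bracket the possibilities.

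*Pattern A: only the spike fraction changes.* Non-spike readings have mean 15 and SD 3 to 5 mmHg; spikes are uniform on 30-38 mmHg (mean 34).

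- Mean shift for doubling (10.5% to 21%): 0.105 × (34 − 15) = 2.0 mmHg. For tripling (to 31.5%): 0.21 × 19 = 4.0 mmHg.
- Variance at spike rate p and SD 3: (1 − p) × 9 + p × 8²/12 + p(1 − p) × 19². This gives 42.5 at 10.5%, 68.1 at 21% and 85.7 at 31.5%.
- Standard error of the difference: √[(42.5 + 68.1)/18] = 2.48 for doubling and √[(42.5 + 85.7)/18] = 2.67 for tripling. The shifts are 0.8 and 1.5 standard errors, against a critical value of about 2.03.
- Simulation (20,000 trials, SD 3 and 5): t-test about 10-12% for doubling and 26-30% for tripling; Mann-Whitney about 8% and 18%. Moving the base to mean 16, SD 3 or mean 20, SD 4 leaves the results in much the same range.

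*Pattern B: the whole distribution shifts.* Normal with mean 18, or log-normal with median 18, scaled so that 10.5% of control eyes reach 30 mmHg.

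- Shift in SD units: z(0.895) − z(0.79) = 0.447 for doubling and z(0.895) − z(0.685) = 0.772 for tripling.
- Detection with 18 per arm: 24-26% and 58-61%.

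**Is the mmHg scale the cause?** The same alternatives were tested on the spike proportion itself with a two-sided Fisher test, by exact enumeration.

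| True change in spike rate | mmHg, pattern A | mmHg, pattern B | Fisher on spikes |
|---|---|---|---|
| 10.5% to 21% | 8-12% | 24-26% | 6.5% |
| 10.5% to 31.5% | 18-30% | 58-61% | 22% |

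With 2/18 spikes on control, Fisher needs 9/18 on PRO-149 to reach p ≤ 0.05 (8/18 gives p = 0.060). For 80% power a comparison of proportions needs 188 per arm for doubling and 58 for tripling. Non-inferiority on the cited trial's margin of 0.13, with both true rates at 10.5% and one-sided 0.05, needs (1.645 + 0.842)² × 2 × 0.105 × 0.895 / 0.13² = 68.8, so 69 per arm. The shortage is in the number of eyes, whichever scale is tested.

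**What an interval would show.** Wilson 95% limits are 3.1% to 32.8% for 2/18 and 16.3% to 56.3% for 6/18. Newcombe's method combines them for 2/18 v 6/18:

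- Lower: 0.222 − √[(0.333 − 0.163)² + (0.328 − 0.111)²] = −0.05.
- Upper: 0.222 + √[(0.563 − 0.333)² + (0.111 − 0.031)²] = +0.46.

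For 2/18 v 4/18 the interval is −14 to +35 points.

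**The case against.** Several points on the other side are sound.

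- **Spikes are captured.** Each reading of 30 mmHg or more is an adverse event, recorded with its diagnosis (8.5.1), and adverse-event incidence is compared by arm. Since 92% of events in the cited trial were such readings, the pooled comparison might largely follow spikes. This stands in part. Here cell or flare grades of 3 or more are also reportable events (7.4.4.5), as is any other untoward occurrence, and the outcome remains secondary and outside the safety rule.
- **Section 10.1.2 also asks for ranges,** so each arm's highest IOP will be seen. A maximum does not give a rate.
- **The rule mentions clinical as well as statistical difference.** An excess of spikes could fail it, but with no definition nothing obliges that reading.
- **This is a pilot.** That is a fair reason not to demand power, but the plan still draws a conclusion of safety from these tests.

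A reader might go further and infer that a mmHg analysis cannot show a rise in spikes, and that this is why a doubled or tripled rate would pass. The documents do not support that. Extra spikes move both means and ranks; a tripling that accompanies a general shift is detected about 60% of the time; and the spike proportion tested by Fisher misses a tripling in 78% of trials. Replacing the mmHg test with a spike test would not cure the problem.

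**Conclusion.** The point holds in a limited form. The primary IOP analysis and the safety rule omit the one pressure measure that the protocol marks as harm, and at 18 eyes per arm a non-significant mmHg result is weak evidence about it. A doubled spike rate would go undetected in roughly 74-92% of trials and a tripled rate in roughly 39-82%, across the two patterns. The main causes are the sample size and treating non-significance as safety; the choice of scale is a lesser part.

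The omission itself rests on the text alone. The percentages rest on assumed IOP distributions, on spikes at one visit, and on a 10.5% rate from a trial whose IOP schedule is not in the documents and whose cell-count follow-up ran to 3 months. They show the order of size and are not predictions for this trial.

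**What to change.** 1. In Table 3 and section 10.1.2, add a pre-specified estimate by arm of the proportion of eyes with any post-operative IOP of 30 mmHg or more, over Days 1, 8 and 29 and any unscheduled reading. Give the difference between arms with a 95% Newcombe or exact interval. Present it as estimation, not as a tested co-primary outcome, which this sample could not support.
2. Keep the mmHg comparison.
3. In the safety rule of 10.1.2, state that IOP safety may not be concluded from a non-significant mmHg comparison alone, and that the conclusion must report the increase in spike rate that the interval does not exclude. For 2/18 v 6/18 that would be up to 46 points.

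The cost is one table, with the scheduled readings already collected, and a few lines of wording. The drawback is that the interval will be wide, so the IOP conclusion will read as less favourable than a bare statement of no difference.
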